7.2 Secondary outcome measures

- Plasma concentrations of incretins (GLP-1 and GIP) and its time profiles during MTT
- OGTT calculations and modelling describing beta cell response to oral glucose load; insulin and c-peptide areas under the curve during OGTT

- Change in gut permeability (Lactulose/Mannitol Test)

Medizinische Universität Graz

- Weight loss will be reported as percentage of excess body weight loss (%EBWL) 4 and 36 weeks after EndoBarrier[™] implantation as well as 6 months after removal of the EndoBarrier[™]
- Changes in cardiovascular risks (non-fatal and fatal coronary heart disease, fatal coronary disease, non-fatal and fatal stroke as well as fatal stroke)
- Changes in gut microbiota

8. STUDY DESIGN

This is an open, single-centre, prospective, single-arm pilot study evaluating the effect of EndoBarrier[™] implantation on insulin sensitivity and beta-cell function in obese patients with type 2 diabetes. 12 subjects will be included in this pilot trial. The investigations will be performed at Medical University of Graz, Department of Internal Medicine, Division of Endocrinology and Metabolism and Division of Gastroenterology and Hepatology.

At baseline all subjects will undergo Dual-energy X-ray absorptiometry (DEXA) measurement, Botnia clamp, blood sampling as well as a meal tolerance test (MTT) and a Lactulose/Mannitol test to determine gut permeability. 4 Weeks, 36 weeks as well as 62 weeks after EndoBarrier[™] implantation all subjects will undergo the above-named tests and investigations, again. Additionally at the baseline visit as well as after one year, tissue samples and intestinal content will be collected endoscopically. This pilot trial limited in size and scope will give us insight into the actions, efficacy and safety of the EndoBarrier[™]. The results of this pilot trial will help us in calculating the sample size for a further planned trial comparing the EndoBarrier[™] against other established weight loss interventions.

8.1 Duration of Study

It is anticipated that the study will run for 30 months (from first patient first visit until last patient last visit).

8.2 Source Data

Source documents comprise the CRF and hospital records, laboratory records and correspondence. All documents will be stored safely in a confidential manner. The subject will be referred to by a unique study subject number/code, their initials and date of birth on all study-specific documentations. The only exceptions will be the signed Consent Forms, Subject Identification log and subject clinical file, all of which will be stored securely by the clinical site.

Source data will be made available for internal and external audits or inspections by regulatory authorities to authorised personnel only.

9. SELECTION AND WITHDRAWAL OF STUDY SUBJECTS

9.1 Subject Selection and Recruitment

The study population will consist of 12 subjects with type 2 diabetes mellitus and a BMI between 30 and 49kg/m². Patients will be identified from the outpatient clinic at the Department of Endocrinology and Metabolism, via Primary Care and adverts.

9.2 Inclusion Criteria

- Participant is willing and able to give informed consent for participation in the study.
- Male or female, aged 18 70 years.
- Type 2 diabetes
- BMI 30-49 kg/m²
- HbA1c ≥ 6.5% (48 mmol/mol)
- Appropriate life style intervention measures have been tried but have failed to achieve or maintain adequate, clinically beneficial weight loss for at least 6 months
- Person is generally fit for intervention
- Person commits to the need for long-term follow-up

9.3 Exclusion Criteria

- Type 1 diabetes mellitus
- Maturity Onset Diabetes of the Young (MODY)
- Secondary diabetes due to a specific disease or glucocorticoid therapy
- Pregnancy or women of childbearing age without adequate contraception
- Women who are breast-feeding
- Hypothalamic cause of obesity, Cushing syndrome
- Major psychiatric disease including diagnosed eating disorders, history of drug or alcohol abuse
- History of bariatric surgery or complex abdominal surgery
- Inflammatory bowel disease
- Pancreatitis
- Cholelithiasis
- Uncontrolled gastroesophageal reflux
- Known upper GI bleeding conditions, e.g. gastric or esophageal varices
- Congenital or acquired abnormalities of the upper GI tract, e.g. stenosis

• Subjects with or a history of coagulopathy, upper gastro-intestinal bleeding conditions such as esophageal or gastric varices, congenital or acquired intestinal telangiectasia

Medizinische Universität Graz

- Chronic non-steroidal anti-inflammatory drug (NSAID) or aspirin treatment (Subjects unable to discontinue NSAIDs (non-steroidal anti-inflammatory drugs) during the implant period)
- Previous GI surgery that could affect the ability to place the device or the function of the implant
- GLP-1 receptor agonist therapy
- Known ischaemic heart disease or heart failure
- History of stroke
- Active Helicobacter pylori (Note: Subjects may be enrolled if they had a prior history of Helicobacter Pylori and were successfully treated)
- Actual iron deficiency anemia
- Subjects or Family history of a known diagnosis or pre-existing symptoms of systemic lupus erythematosus, scleroderma or other autoimmune connective tissue disorder
- Known malignancy or any other multimorbid patient condition or circumstance, which, in the opinion of the investigator, would affect the patient's ability to participate in the protocol or would put the participant at an unjustified risk

9.4 Withdrawal/Drop out of subjects

Each subject has the right to withdraw from the study at any time without prejudice or compromise to future care.

The investigator may discontinue or withdraw the subjects under the following circumstances:

- Significant protocol deviation
- Significant non-compliance with treatment regime or study procedures
- An adverse event that requires discontinuation of the study medication or results in inability to continue to comply with study procedures. If a subject is withdrawn due to an adverse event, the investigator will arrange for follow-up visits or telephone calls until the adverse event has resolved or stabilised.
- Consent withdrawn
- Lost to follow up
- The study will be stopped prematurely if any information relating to the IMP or any other aspect of the study arises that may cause harm to the participant.
- Any other situation that may, in the opinion of the investigator, make it unsafe or inappropriate for the subject to continue in the trial

9.5 Payment to subjects

Reimbursement of reasonable travel expenses will be considered.

9.6 End of study

The study end is defined as the last visit of the last patient. In the case of new data suggesting a significant safety concern of the device under investigation, the trial will be prematurely stopped.

10 STUDY PROCEDURES

10.1 Schedule of study procedures

	Screening	Baseline			Follow-up						
	V1 (1-14day before V2)	V2	V3 (up to 3 days after V2)	V4 (up to 3 days after V2)	V5 (4 weeks ± 2 week after V4)	V6 (up to 3 days after V5)	V7 (36 weeks ± 3 weeks)	V8 (up to 1 week after V7)	V9 (62 weeks ± 3 weeks)	V10 (up to 1 week after V9)	
Informed Consent	Х										
Inclusion/exclusion criteria	Х	х									
Demography, medical history	x										
Concomitant medication	x	х			Х		x		X		
Vital signs	Х	х			Х		X		X		
Physical examination	Х	х			Х		x		х		
Pregnancy test (females with childbearing potential)	x	х			х		×		х		
Botnia clamp		х			x		x		х		
Blood sampling	x		х			х		x		Х	
Dual-energy X-ray absorptiometry (DEXA)		х			x		x		х		
Electrocardiography (ECG)	х										
Meal tolerance test (MTT)			x			Х		x		Х	
¹³ C-Urea breath test	x										
Bypass liner insertion				х							
Bypass liner removal							х				
Food frequency questionnaire (FFQ)		x			Х		х		х		
Biopsies				Х			Х				
Adverse Events			Х	Х	Х		х		х		
Stool sampling			Х			Х		x		Х	
Lactulose/Mannitol Test			Х			Х		x		Х	
Gastroscopy											
Abdomen Sonography		x									
Liver Elastography											

10.2 Visit Schedule

Visit 1 Screening (14 to 1 day(s) prior to potential enrolment)

Severely obese patients with T2DM are eligible to participate in our study. Those who accomplish the inclusion criteria and none of the exclusion criteria will be enrolled in the trial and submitted to the following investigation procedures in the screening visit, after signing the informed consent:

- Check inclusion and exclusion criteria
- Check for demographic data, medical and surgical history and concomitant medication
- Date of birth, gender, race, smoking status, alcohol consumption,
- Body weight and body height
- Vital signs: resting pulse and blood pressure
- Blood sample for HbA1c
- Baseline safety blood tests (fasting): Full blood cell count, renal function tests, liver function tests
- Physical examination
- Pregnancy test in female woman of childbearing age.
- ¹³C-urea breath test

Visit 2 Baseline

In the morning of the second study visit (V2) the subjects will arrive at the Division of Endocrinology and Metabolism between 07:00 and 08:00 AM of the pre-scheduled day, after at least 8 hours fasting.

During V2, the Botnia-Clamp (testing procedure combining intravenous glucose tolerance test [IVGTT] and hyperinsulinemic-euglycaemic clamp [HEC]) will be performed.

If blood recent blood values (within 6 weeks) are available to confirm the eligibility of a subject at the screening visit, visit 2 may also be performed together with the screening procedures.

As part of this visit the following procedures will be performed:

- Review inclusion and exclusion criteria
- Vital signs: resting pulse and blood pressure
- Body weight
- Physical examination
- Concomitant medication review
- Botnia clamp
- DEXA
- Urinary pregnancy test in female woman of childbearing age
- Gastroscopy
- Abdomen Sonography and Liver elastography
- Diet instructions.

Visit 3 Baseline (up to 3 days after V2)

Study visit 3 will take place not later than 3 days after V2.

Medizinische Universität Graz

The subjects will arrive at the Division of Endocrinology and Metabolism after an overnight fast (at least 8 hours). Meal tolerance test (MTT) will be performed at V3.

Additionally, at Visit 3 subjects will be instructed by a qualified person to consume a liquid diet the first week after EndoBarrier[™] placement, puree diet during the second week, and normal diet (1200 – 1500 kcal/day) combined with exercise and behaviour modification for the remainder of the implant duration. Participants will also be instructed to take a proton pump inhibitor (40mg BID omeprazole) starting 3 days before the implant through 2 weeks after explant. Daily multivitamin and iron supplements will be provided and recommended for use during the 52 weeks of the implant duration.

- Meal tolerance test
- Blood sampling
- Stool sampling
- Lactulose/Mannitol Test

Visit 4 (Implantation of EndoBarrier[™])

Patient preparation

- 1. Patients must be fasting for 8 hours prior to the procedure.
- 2. Patients must be started on a Proton Pump Inhibitor (40mg twice a day) three days before the procedure and continue regimen until two weeks after the device is removed.
- **3.** Spasmolytics may be used.

Sedation

4. The procedure will be performed under conscious sedation.

Procedural Step

5. Insertion will be performed according to manufacturer instructions

Visit 5 (week 4 ± 2 week)

Study visit 5 will take place not later than six weeks after the implantation of the EndoBarrier[™].

- Physical examination
- Vital signs: resting pulse and blood pressure
- Body weight
- Concomitant medication review
- Botnia clamp
- DEXA
- Adverse events assessment

• Pregnancy Test

Visit 6 (up to 3 days after V5)

Study visit 6 will take place not later than 3 days after V5.

- Meal tolerance test
- Stool sampling
- Blood sampling
- Lactulose/Mannitol Test

Visit 7 (36 weeks ± 3 weeks)

Study visit 5 will take place not later than 39 weeks after the implantation of the EndoBarrier[™]. At this

visit the sleeve will be removed.

- Vital signs: resting pulse and blood pressure
- Body weight
- Concomitant medication review
- DEXA
- Adverse events assessment
- Biospies
- Botnia clamp

Visit 8 (up to 1 week after V7)

Study visit 8 will take place not later than 1 week after V7.

- Vital signs: resting pulse and blood pressure
- Body weight
- Concomitant medication review
- Adverse events assessment
- Meal tolerance test
- Stool sampling
- Blood sampling
- Lactulose/Mannitol Test

Visit 9 (62 weeks ± 3 weeks)

Study visit 9 will take place not later than 29 weeks after the removal of the EndoBarrier[™].

• Physical examination

- Vital signs: resting pulse and blood pressure
- Body weight
- Concomitant medication review
- Botnia clamp
- DEXA
- Adverse events assessment
- Pregnancy Test

Visit 10 (up to 1 week after V9)

Study visit 8 will take place not later than 1 week after V9.

- Meal tolerance test
- Stool sampling
- Blood sampling
- Lactulose/Mannitol Test
- Study end

Safety visits (after 12, 24 and 48 weeks)

12, 24 and 48 weeks after implantation safety visits will be carried out. As part of these visits blood samples (8ml) will be taken for safety measurements (including blood cell count, iron status, liver function). Additionally, the body weight will be recorded.

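### Followed as written, the visit windows leave 1 to 2 days between the omeprazole instruction at Visit 3 and implantation at Visit 4, against a mandatory 3-day lead-in

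*Protocol*

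**What the plan says.** **Lead-in.** Protocol section 10.2 places the omeprazole instruction (40 mg twice daily) under Visit 3, with the timing "starting 3 days before the implant through 2 weeks after explant". The Visit 4 preparation list repeats the rule in binding terms: "Patients must be started on a Proton Pump Inhibitor (40mg twice a day) three days before the procedure". Section 12.3 states it again, equally firmly.

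**Windows.** For the baseline meal-test visit, section 10.2 says "Study visit 3 will take place not later than 3 days after V2". The implantation window appears only in the column header of the table in section 10.1: "V4 (up to 3 days after V2". Section 10.2 gives no window for Visit 4.

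**Fasting and tests.** Participants attend Visit 3 "after an overnight fast (at least 8 hours". That visit includes a liquid meal (section 11.1), stool sampling and a 5-hour urine collection for lactulose/mannitol (section 11.7). For Visit 4, "Patients must be fasting for 8 hours prior to the procedure".

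**Medication review.** Concomitant medication is reviewed at Visits 1, 2 and 5 and at later visits. No review is listed at Visit 3 or Visit 4.

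**Use of the data.** The SAP derives the early insulin response from the meal test and makes its change from baseline to 4 and 36 weeks a primary endpoint. Changes in the lactulose/mannitol ratio and in meal-test glucose AUC are secondary endpoints.

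**The concern.** An instruction cannot be followed if it is first given after the dosing should have begun. The table allows too little time between Visit 3 and Visit 4 for a 3-day course to start at Visit 3. A site that follows the text visit by visit would breach a pre-procedure precaution that the protocol states as compulsory.

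The conflict can be resolved in more than one way, and the protocol does not choose. One site practice would shorten the lead-in, with the Visit 3 tests done off protocol omeprazole. Another would start dosing earlier, with those tests done on it. Visit 3 supplies the only pre-implant meal and permeability tests and the only pre-implant stool sample. In a single-arm study of 10 (SAP) or 12 (protocol) participants, every result is a change from baseline, so the baseline conditions should be the same for everyone and should be recorded.

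**Working it through.** The plan's own figure is the required lead-in of 3 days. It is a stated requirement, not a calculation, so the check is whether the windows can deliver it.

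**Inputs.** Count whole days with Visit 2 as day 0.
- Visit 3 is on day 1, 2 or 3. Day 0 is excluded because Visit 2 is a morning clamp with glucose infusion and Visit 3 needs a separate overnight fast.
- Visit 4 is on a later day than Visit 3. A same-day procedure would need an 8-hour fast beginning after the meal drink, with a 5-hour urine collection under way. If it were allowed, the gap would be 0 days, which is worse.
- Gap = Visit 4 day − Visit 3 day. An instruction first given at Visit 3 complies if the gap is at least 3.

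**Header read literally (Visit 4 no later than day 3).**

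| Visit 3 | Visit 4 | Gap | Latest compliant start (Visit 4 − 3) |
|---|---|---|---|
| day 1 | day 2 | 1 | day −1 |
| day 1 | day 3 | 2 | day 0 |
| day 2 | day 3 | 1 | day 0 |

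The gap reaches 3 in 0 of 3 pairs. Visit 3 on day 3 is allowed by its own window but leaves no day for Visit 4.

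**Dosing from Visit 2 (day 0).** The lead-in equals the Visit 4 day, so it is met when Visit 4 is on day 3, which is 2 of 3 pairs. Implanting on day 2 would need a start the day before the Visit 2 clamp. In every row, the latest compliant start is 1 or 2 days before Visit 3, so the Visit 3 tests would be done on omeprazole.

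**Header read as a slip for a window of up to 3 days after Visit 3.** Three Visit 3 days times gaps of 1, 2 or 3 give 9 pairs. The gap is 3 only in (1,4), (2,5) and (3,6), which is 3 of 9. Even then, the text does not say whether the first dose comes before or after that day's tests.

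**Window of 3 to 7 days after Visit 3.** Three Visit 3 days times five gaps give 15 pairs. All 15 comply, with Visit 4 on days 1 + 3 = 4 to 3 + 7 = 10.

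These are counts of permitted day pairs, not probabilities.

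**The case against.** The strongest reply is that the rule does not contradict itself. The lead-in is tied to the implant, not to Visit 3, and is stated again where the procedure is prepared. A Visit 2 start with implantation on day 3 satisfies every window. Nothing bars an instruction at Visit 2, which already lists "Diet instructions". The header is probably a copying slip: it repeats the Visit 3 window, and section 10.2 has similar slips, such as wrong visit numbers in the text under Visits 7 and 10.

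Much of this stands. A reader might infer that compliance is impossible; it is not. But the protocol does not schedule the route that works, and correcting the slip helps only at the upper limit of the window.

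Three other stronger readings are tempting but unsupported.
- **That the study intervention's status at baseline is open.** Omeprazole is a protocol-required co-medication; the investigational product is the liner.
- **That baseline results are biased.** The documents give no omeprazole effect on any endpoint.
- **That its use would go unrecorded.** Existing use should be caught by the Visit 1 and Visit 2 reviews, and the Visit 5 review might recover the start date. What is missing is a check at Visit 3, when status at the baseline tests is in question.

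It is also fair to say that testing off omeprazole at baseline is not plainly better, because follow-up tests during the implant period are on it. The fix sets out that choice.

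**Conclusion.** The point holds as a minor scheduling conflict. Under the literal header, an instruction first given at Visit 3 falls 1 to 2 days short of the 3-day lead-in (3 − 2 = 1, 3 − 1 = 2) in every permitted pair. Under the more generous reading, it complies only at a gap of exactly 3 days. The plan also leaves unstated whether the Visit 3 tests are done on or off omeprazole.

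This rests on three assumptions: whole-day counting, Visits 2, 3 and 4 on separate days, and participants first hearing the instruction at Visit 3, where the text puts it. If sites routinely instruct at Visit 2 and implant on day 3, the precaution is met, and what remains is the unscheduled practice and the unstated condition of the baseline tests.

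**What to change.** 1. In the section 10.1 table, set Visit 4 at least 3 days after Visit 3, for example 3 to 7 days.
2. Keep the instruction at Visit 3, and state that the first dose follows completion of that visit's meal, stool and lactulose/mannitol tests.
3. Add a concomitant-medication check at Visit 3. The exclusion criteria do not bar existing acid-suppressant use, so this should be recorded too.

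**Cost.** This needs a header change, one sentence and one extra check. Implantation moves from days 2 to 3 after Visit 2 to days 4 to 6 at a 3-day gap, or up to day 10 with the wider window. Follow-up intervals do not move: the table gives "V5 (4 weeks ± 2 week after V4", and section 10.2 counts Visit 7 from implantation.

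**Downside.** Baseline is then off protocol omeprazole while Visits 6 and 8 are on it, since the course runs to 2 weeks after removal and Visit 8 is within 1 week of Visit 7. This touches the meal-test early insulin response, a primary endpoint in the SAP. The clamp is in the same position (Visit 2 off, Visits 5 and 7 on). Visit 10 is off again: the earliest Visit 9 is week 59 and the latest course end is 39 + 2 = week 41, at least 18 weeks before. State this when changes are reported.

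**Alternative.** If the sponsor prefers baseline matched to the implant period, start omeprazole at or before Visit 2 for everyone. A start at Visit 2 needs Visit 4 on day 3 or later. Matching the clamp as well needs a start before Visit 2, which would precede consent for participants whose Visit 2 is combined with screening, so they would need separate visits.

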6.2 Secondary objectives

- To assess the beta cell insulin response to oral and intravenous glucose loads early (4 weeks) and 9 months after EndoBarrier[™] implantation as well as 6 months after removal of the duodeno-jejunal bypass device.
- To assess changes in body weight from baseline to 9 and 15 months, respectively.
- To determine changes in gut permeability and gut microbiota from baseline to 9 and 15 months, respectively.
- To investigate changes in incretin hormone levels during the meal tolerance test (MTT) from baseline to 9 and 15 months, respectively.
- To evaluate changes in area under curve (AUC) of glucose from baseline to 9 and 15 months, respectively.
- To assess changes in body composition assessed by dual energy x-ray absorptiometry (DEXA) from baseline to 9 and 15 months, respectively.
- To evaluate correlations between MTT and Botnia clamp results regarding insulin sensitivity and beta-cell function
- To determine changes in cardiovascular risk as assessed by the UKPDS risk engine from baseline to 9 months and 15 months, respectively.

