- Previous GI surgery that could affect the ability to place the device or the function of the implant
- GLP-1 receptor agonist therapy

- Known ischaemic heart disease or heart failure
- History of stroke
- Active Helicobacter pylori (Note: Subjects may be enrolled if they had a prior history of Helicobacter Pylori and were successfully treated)
- Actual iron deficiency anemia
- Subjects or Family history of a known diagnosis or pre-existing symptoms of systemic lupus erythematosus, scleroderma, or other autoimmune connective tissue disorder
- Known malignancy or any other multimorbid patient condition or circumstance, which, in the opinion of the investigator, would affect the patient's ability to participate in the protocol or would put the participant at an unjustified risk

Clinical endpoints

Primary endpoints

- Change in the glucose infusion rate (Botnia Clamp) adjusted for body weight at baseline from baseline to 4 and 36 weeks after the Endobarrier implantation, respectively
- Change in early insulin response from baseline to 4 and 36 weeks after the Endobarrier implantation, respectively

Secondary endpoints

- Change in the glucose infusion rate (Botnia Clamp) adjusted for body weight at baseline from baseline to 24 weeks after the Endobarrier explantation
- Change in early insulin response from baseline to 24 weeks after the Endobarrier explantation, respectively
- Change in body mass index from baseline to 4 and 36 weeks after the Endobarrier implantation and 24 weeks after the Endobarrier explantation
- Change in body weight from baseline to 4 and 36 weeks after the Endobarrier implantation and 24 weeks after the Endobarrier explantation
- Change in HbA1c from baseline to 4 and 36 weeks after the Endobarrier implantation and 24 weeks after the Endobarrier explantation
- Change in lactulose/mannitol ratio from baseline to 4 and 36 weeks after the Endobarrier implantation and 24 weeks after the Endobarrier explantation
- Change in glucose AUC (MMT) from baseline to 4 and 36 weeks after the Endobarrier implantation and 24 weeks after the Endobarrier explantation
- Change in c-peptide AUC (MMT) from baseline to 4 and 36 weeks after the Endobarrier implantation and 24 weeks after the Endobarrier explantation
- Change in UKPDS CHD risk from baseline to 4 and 36 weeks after the Endobarrier implantation and 24 weeks after the Endobarrier explantation

Sample Size

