This study is planned as a mechanistic pilot trial to gather first data about the parameter outlined in the primary and secondary parameter section. Currently, insufficient data are available on parameters for estimating the sample size required for this pilot trial. However, previous pilot trials investigating measurements of glucose metabolism with EndoBarrier[™] have used 10-16 subjects to demonstrate improvements[25, 26]. Therefore, we aim to include 10 subjects in our trial.

Statistical Analyses

Time of statistical analysis

All statistical analyses will be performed after the completion of trial and dataset closing.

Analysis population

All analyses will be performed on the 'Intention to treat (ITT)' or 'full analysis set' population. All patients who will be randomized to treatment sequences will be considered for the ITT analysis.

Data inspection

Data will be received in Microsoft Excel format and will be imported into statistical softwares for the analysis. First, data will be inspected for data entry errors on 10% of randomly selected data. Afterwards, data will be inspected for outliers and implausible values and these data points will be verified from the clinical report forms.

Summarization of data

Qualitative variables will be summarized as frequency with corresponding percentage (%), while quantitative variables will be summarized as either mean ± standard deviation (SD) or median and interquartile range (IQR) as appropriate. Both quantitative and qualitative variables will be presented in the table.

Statistical procedures

Normality of quantitative variables will be assessed using Shapiro-Wilk tests. The choice of statistical procedures for both primary and secondary quantitative endpoints will depend upon the distribution of variables. If normality assumption is violated, no data transformation will be carried out.

The early insulin response will be estimated from the MMT using the formula (30 minutes insulin – basal insulin)/(30 minutes glucose). The AUCs are determined by the trapezoidal method. Based on IVGTT measurements, the incremental trapezoidal area of insulin and C-

peptide during the first 10 minutes after glucose administration will represent the firstphase insulin response or acute insulin response (AIR). AIR will be also measured as the sum of insulin and C-peptide concentrations during the first 10 minutes after the glucose challenge.

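### The 36-week early insulin response, a primary endpoint in the SAP, is measured after the liner has been taken out, as are the other 36-week meal-test, permeability and stool measures

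*Protocol*

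**What the plan says.** **Removal.** Protocol 10.2 sets Visit 7 (V7) at 36 ± 3 weeks and says that at this "visit the sleeve will be removed". The table in Protocol 10.1 also marks removal at V7. The Botnia clamp, DEXA and biopsies are listed for the same visit, and the order of clamp and removal is not given.

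**Meal test, permeability, stool and blood.** These are listed at V8 and not at V7, in both the table and the visit list: "Study visit 8 will take place not later than 1 week after V7".

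**Endpoints.** One of the SAP's two primary endpoints is "Change in early insulin response from baseline to 4 and 36 weeks after the Endobarrier implantation, respectively". Under Statistical procedures the SAP fixes the source: "The early insulin response will be estimated from the MMT using the formula". Its secondary endpoints include "Change in lactulose/mannitol ratio from baseline to 4 and 36 weeks after the Endobarrier implantation", and the glucose and C-peptide AUCs from the same meal test at the same times. Protocol 7.2 adds the incretin profiles during the meal test.

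**Objectives.** The first secondary objective in Protocol 6.2 sets a time "9 months after EndoBarrier" implantation against a separate time 6 months after removal. The SAP keeps the same distinction, at 36 weeks after implantation and 26 weeks after removal.

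**The concern.** Protocol 12.1 describes the device as a physical barrier between food and the intestinal wall. A meal test shows that effect directly only while the barrier is in place. Once the liner is out, the meal test describes the early post-removal state, although the endpoint's name suggests the end of the implant period.

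Three things are at stake:

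- **Persistence.** If early insulin response has fallen back by the 36-week reading, the effect may have faded on the device or gone when it was removed. The data cannot separate the two. Protocol section 4 names persistence after removal as an open question.
- **Permeability.** The SAP introduction asks whether the liner causes a leaky gut. The 36-week lactulose/mannitol test follows endoscopic removal and biopsies by 0 to 7 days, so a rise could come from the procedure.
- **Oral against intravenous response.** If the V7 clamp is done before removal, comparing or correlating the meal test with the clamp at 36 weeks pairs an off-device value with an on-device one.

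**Working it through.** This is a check of visit order and calendar arithmetic. No power or sample-size formula applies.

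**1. Does the schedule place removal at week 36?**

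- Protocol 10.2 requires V7 by week 39: 36 + 3 = 39, which agrees.
- V9 (62 ± 3 weeks) must fall within 29 weeks of removal: 62 + 3 − 36 = 29, which agrees. Removal at week 52 would give 62 + 3 − 52 = 13, which does not.
- The SAP objectives use week 62 and 26 weeks after removal: 62 − 26 = 36, which agrees. The SAP endpoint list says 24 weeks after explantation. That gives 36 + 24 = 60, inside the V9 window of 59 to 65 weeks.

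**2. When does V8 fall?** V8 is V7 plus 0 to 7 days. Nominally that is weeks 36 to 37, and across the windows it runs from week 33 to 39 + 1 = 40. There is an upper limit but no minimum interval, so time off the device can differ between subjects by up to a week.

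**3. Which measures have a late value with the liner in place?**

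| Measure | Before implant | Early, liner in place | Late, liner in place | After removal |
|---|---|---|---|---|
| Meal test (early insulin response, glucose and C-peptide AUC, incretins) | V3 | V6 | none | V8, V10 |
| Lactulose/mannitol, stool | V3 | V6 | none | V8, V10 |
| Botnia clamp (glucose infusion rate, acute insulin response) | V2 | V5 | V7, only if done before removal | V9 |

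Between V6 and V7 there are only the safety visits at weeks 12 and 24, which take safety bloods and body weight.

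**4. How much of the implant period is unobserved?** V5 falls in weeks 2 to 6 and V6 up to 3 days later, so V6 lies between week 2 and week 6 + 3/7 = 6.43.

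- Nominal: 36 − 4 = 32 weeks
- Shortest: 33 − 6.43 = 26.6 weeks
- Longest: 39 − 2 = 37 weeks

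**5. Share of the primary analysis.** Two primary endpoints at two times give 2 × 2 = 4 contrasts. Early insulin response at 36 weeks is off device, so 1 of 4 is affected. The glucose infusion rate at 36 weeks comes from the V7 clamp and its device state is unstated.

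**6. Comparison with baseline.** There the order is the other way round: the V3 tests are listed before implantation at V4.

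**The case against.** **The protocol is not consistent on implant length.** Section 10.2 also refers to 52 weeks of implant duration, section 8 has endoscopic sampling after one year, and section 16 says removal is mostly after 1 year. With a 52-week implant, a test at week 37 would be on device. These passages must be reconciled. They do not undo the finding, because both the table and the visit list assign removal to V7 and the arithmetic in step 1 fits only that.

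**The label is literally true.** V8 is about 36 weeks after implantation, and neither document says that the 36-week value must be on device. That intent is inferred, from the objectives' split between time after implantation and time after removal and from the baseline order. Even so, neither document discloses that the test follows explantation.

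**Much of the main data is less affected.** This is right. The protocol's primary variable, acute insulin response, and the SAP's glucose infusion rate both come from the V7 clamp, a fasting intravenous test to which the meal mechanism does not apply in the same way. Protocol 11.6 says stool does not represent the small intestine, and the endoscopic samples are taken at removal. That section also puts stool sampling loosely at the time of removal, which should be reconciled with V8, but it does not put it before removal. Slow markers such as HbA1c would change little in a week.

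**The procedural effect on permeability is not demonstrated.** No figure in the documents supports it. It stands as a possible confounder that this visit order cannot exclude.

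**It is an exploratory pilot.** Its stated purposes are mechanism and planning later trials, and both depend on knowing the device state at each measurement.

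**Conclusion.** The concern holds. Under the schedule as written, every subject who follows it has the 36-week meal test, lactulose/mannitol test and stool sample taken 0 to 7 days after the liner is out. One of the four primary contrasts is affected. Four SAP endpoints (early insulin response, glucose AUC, C-peptide AUC and lactulose/mannitol ratio), plus stool microbiota and the protocol's incretins, have a single on-device value at about week 4.

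This rests on removal taking place at V7, as the schedule states, and on the 36-week value being meant to describe the implanted state. It does not extend to the V7 clamp measures. For those the only gap is that the order of clamp and removal is not specified.

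**What to change.** **If V7 and V8 have not yet taken place:**

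- In Protocol 10.1 and 10.2, move the meal test, lactulose/mannitol test, stool and blood sampling from V8 to within 1 week before the V7 removal, mirroring V3 before V4.
- State that the V7 clamp is done before sedation and removal.
- Reconcile the texts on implant duration (sections 8, 10.2 and 16) and on stool timing (section 11.6) with the schedule.

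The removal date does not change. Two existing visits swap order, with no added visit, sample or procedure. The cost is a protocol amendment, with ethics approval where section 16.2 requires it.

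**If the data are already collected** (the documents do not say):

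- In the SAP, rename the affected 36-week endpoints as 0 to 7 days after explantation.
- Report days since removal for each subject.
- Base claims about meal-test or permeability effects with the liner in place on week 4 only.
- Report the actual order of clamp and removal at V7.

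The cost is relabelling and a narrower claim.
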